6.8.4. Treatment after Study Completion

Study interventions will not be made available to study participants after Visit 31 (Week 52) or after the participant's early discontinuation from study treatment.

At the last treatment visit (Visit 31 [Week 52] or ED visit), the investigator will determine participant's transition from study treatment to another non-study diabetic treatment. The investigator may prescribe a non-study basal insulin for use during the safety follow-up period. Participants will continue their concomitant non-insulin antihyperglycemic medications at the discretion of the investigator and continue to monitor their FBG and complete the e-diary.

Study participants treated with LY3209590 transitioning to a non-study basal insulin:

Study participants will receive the last injection of LY3209590 at Week 52 of the study and can begin the transition to the non-study insulin after Visit 31 (Week 52). At Visit 31 (Week 52), the investigator will review the instructions for transitioning to the non-study insulin. During this transition period, the participant's FBG should be used to guide dose initiation and adjustment for the insulin prescribed for the safety follow-up period.

No daily basal insulin will be required until the FBG is above 120 mg/dL (6.6 mmol/L) for 2 consecutive measurements. The prescribed non-study daily basal insulin should be started at a dose of 10 units/day and adjusted based on FBG and the investigator judgement in accordance with any country-specific label. The initial prescribed dose and any dose adjustments made for the non-study insulin during the safety follow-up period should be documented in the eCRF. An unscheduled visit in addition to Visit 801 may occur during this time to facilitate the transition to the non-study daily basal insulin.

Since LY3209590 has a half-life of approximately 17 days, a careful titration of the daily basal insulin is necessary to prevent hypoglycemia due to overlapping insulin action. Therefore, the investigator should consider titrating the daily insulin to reach 50% of the required daily dose at approximately 2-weeks and 80% at approximately 4-weeks.

Study Participants treated with insulin degludec transitioning to a non-study basal insulin:

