7.1. Discontinuation of Study Intervention

When necessary, a participant may be **permanently discontinued** from study intervention. If so, the participant will remain in the study and follow procedures for remaining study visits, as shown in the SoA.

Participants who stop the study intervention permanently may receive another glucose-lowering medication. The new glucose-lowering medication will be recorded on the CRF for antihyperglycemic medications.

A participant should be **permanently discontinued** from study intervention if

- the participant becomes pregnant during the study
- the participant requests to discontinue study intervention
- the participant is diagnosed with an active or untreated malignancy, except for successfully treated basal or squamous cell carcinoma
- the participant did not take insulin degludec for more than 21 consecutive days or missed more than 3 consecutive doses of LY3209590 at any time during the study, or
- in the opinion of the investigator, the participant should permanently discontinue the study intervention for safety reasons.

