Participant-reported hypoglycemia	The baseline period is the lead-in period prior to the first dose date of study treatment.	
 Treatment period starts on the first dose date of study treatment and ends 
 At Week 52 (Visit 31) if completed treatment on the last dose date of study treatment + 10 days for LY3209590, +1 day for degludec if discontinued study treatment early Post-treatment period starts from 
 Week 52 (Visit 31) +1 day if completed treatment last dose date of treatment +11 days for LY3209590, +2 days for degludec if discontinued study treatment early and ends on the last date in the study
TEAEs	The baseline period includes the screening/lead-in period up to the first dose of study treatment (The AE Start Relative to Exposure Assessment CRF is used to determine).	Safety analysis period starts after the first dose and ends at the last visit in the study including safety follow-up period.
Safety laboratory tests, vital signs, and body weight	
The baseline will be the last non-missing assessment prior to or on the first dose date of study treatment
 
Planned measurements at scheduled visits will be included.
	
 All scheduled visits after the first dose date up to Visit 802 for MMRM or ANCOVA 
Planned measurements at scheduled visits will be included.

laboratory values elevated or low, vital signs and body weight categorical measures	
Starts from the screening visit and ends prior to or on the day of first dose of study treatment .
 
All available measurements at scheduled and unscheduled visits will be included. The baseline for weight will be the last non-missing value during the baseline period.
	
Starts after the day of first dose of study treatment and ends at the last visit in the study including both treatment period and follow-up period.
 
All available measurements at scheduled and unscheduled visits in the specified analysis period will be included.

Analysis	Baseline Observations	Post-Baseline Observations
Anti-LY3209590 antibody	Refer to PSAP	Refer to PSAP
Patient-reported outcomes	The baseline will be the data collected at Visit 3	
 • All scheduled visits after Visit 3 • Last collection after Visit 3

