Event rate of Level 2 hypoglycemia events (events/participant/year): • All documented	Baseline, 0-6, 0-12, 0-26, 0-52, 12-26, 26-52 weeks, post-treatment period	Negative binomial regression with treatment and baseline HbA1c as covariates, log (exposure/365.25 days) as the offset in the model. If the number of events is too small to run the negative binomial regression, exposure adjusted rate calculated by total number of events divided by total exposure for individual patients will be provided and the empirical method (see Appendix 9 [Section 6.9] for details) will be used for treatment comparison.
Event rate of Level 3 hypoglycemia events (events/participant/year): • All documented	baseline, 0-26, 0-52, 26-52 weeks, post-treatment period	Negative binomial regression with treatment and baseline HbA1c as covariates, log (exposure/365.25 days) as the offset in the model. If the number of events is too small to run the negative binomial

Endpoint	Analysis Period	Statistical Method
		regression, exposure adjusted rate calculated by total number of events divided by total exposure for individual participants will be provided and the empirical method (see Appendix 9 [Section 6.9] for details) will be used for treatment comparison.
Event rate of Level 2/3 hypoglycemia events (events/participant/year): 
 • All documented • Nocturnal • Non-nocturnal 	baseline, 0-6, 0-12, 0-26, 0-52, 12-26, 26-52 weeks, post-treatment period	Negative binomial regression with treatment and baseline HbA1c as covariates, log (exposure/365.25 days) as the offset in the model. If the number of events is too small to run the negative binomial regression, exposure adjusted rate calculated by total number of events divided by total exposure for individual patients) will be provided and the empirical method (see Appendix 9 [Section 6.9] for details) will be used for treatment comparison. The plots of the mean cumulative functions (MCFs) by each treatment arm will also be created. The population mean for cumulative number of events up to time t, $M(t)$, will be estimated using a nonparametric estimation method described by Nelson (2003).
Incidence of Level 1 hypoglycemia events: 
 • All documented 	Baseline, 0-6, 0-12, 0-26, 0-52, 12-26, 26-52 weeks, post-treatment period	Logistic regression with treatment and baseline HbA1c as covariates.

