Incidence of Level 2 hypoglycemia events: 
 • All documented 	Baseline, 0-6, 0-12, 0-26, 0-52, 12-26, 26-52 weeks, post-treatment period	Logistic regression with treatment and baseline HbA1c as covariates.
Incidence of Level 3 hypoglycemia events: 
 • All documented 	Baseline, 0-26, 0-52, 26-52 weeks, post-treatment period	Logistic regression with treatment and baseline HbA1c as covariates.
Incidence of Level 2/3 hypoglycemia events: 
 • All documented 	Baseline, 0-6, 0-12, 0-26, 0-52, 12-26, 26-52 weeks, post-treatment period	Logistic regression with treatment and baseline HbA1c as covariates.

Endpoint	Analysis Period	Statistical Method

 • Nocturnal • Non-nocturnal 		
Potential persistent-recurrent hypoglycemia events 
 • identified by investigator • identified by pre-specified criteria (defined in Appendix 10 [Section 6.10]) 	Safety analysis period (see definition in Section 4.6)	The number of participants with at least one event will be summarized and compared by Fisher's exact test. The number of events will also be provided. Listings of the events will also be provided.

Abbreviations: HbA1c = hemoglobin A1c; Level 2/3 = Level 2 and Level 3 composite.

Note: The hypoglycemia yearly rate during defined period is calculated by the number of hypoglycemia within the period/number of days patient at risk within the period * 365.25. For rare events, 100-year rate will be provided. The hypoglycemia incidence during defined period indicates if the patient has at least 1 hypoglycemia events within the period (Yes/No).

Note: For treatment group comparison at baseline, baseline HbA1c is not included in the model.

A sensitivity analysis will be done for selected hypoglycemic endpoints where all hypoglycemic events are considered one hypoglycemic event until a succeeding glucose value is ≥ 70 mg/dL.

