6.6. Appendix 6: Derivation of CGM Variables

Blinded CGM will be worn by participants at the following designated weeks:

- Two weeks in screening/lead-in period with the data download at Visit 3 (Week 0),
- Four weeks after the initiation of study treatment with the data download at Visit 7 (Week 4),
- Four weeks from V7 (Week 4) with the data download at Visit 11 (Week 8) (only for sites in Japan),
- Four weeks near the end of weekly titration period with the data download at Visit 15 (Week 12),
- Four weeks near the end of half year treatment with the data download at Visit 24 (Week 26),
- Four weeks near the primary endpoint with the data download at Visit 31 (Week 52), and
- Four weeks after the end of study treatment period with the data download at Visit 802 (Week 57).

Dexcom G6 system will be used in all countries to collect CGM data except China. In China, Libre Freestyle H system will be used instead.

Linear interpolation will be used to impute the missing glucose readings during intervals >7 minutes and ≤ 15 minutes. Missing data will be imputed at a 5-minute interval using the BG value before and the one after the interval.

For example, the BG reading before the interval is 50 mg/dL at time 100 min, and the BG reading after interval is 70 at time 115 min, then the missing records will be imputed as:

- at time 105 min, BG reading= $50+5*(70-50)/(115-100)=56.7$, and
- at time 110 min, BG reading= $50+10*(70-50)/(115-100)=63.3$.

Glucose reading intervals >15 minutes will be treated as missing data and not be counted in the length of the analysis periods. Since the Libre Freestyle H system normally provides readings every 15 minutes, the linear interpolation missing data imputation will not be performed.

As shown in the table below, all the CGM derivations are based on the data from valid CGM periods of a day and sessions unless otherwise specified.

Minimum Data Available to Define a Valid Period of the Day and CGM Session

Period	Definition of Valid Period	Definition of Valid CGM Session
Valid CGM Day (00:00-23:59)	$\geq 70\%$ of expected values available (≥ 202 of 288 values for Dexcom G6 system; ≥ 68 of 96 values for Libre Freestyle H system)	≥ 3 valid CGM days within a visit define a valid CGM visit. A valid CGM session only includes valid CGM visits.

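### The post-treatment period for participant-reported hypoglycemia has no cap, so about 5 weeks from completers is pooled with up to 55 to 57 weeks from early stoppers who stay in the study

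*SAP*

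**What the plan says.** The baseline and post-baseline table in SAP 4.1 sets the post-treatment period for participant-reported hypoglycemia. Completers start at "Week 52 (Visit 31) +1 day if completed treatment". Early stoppers start at the last dose plus 11 days on LY3209590, or on degludec plus "2 days for degludec if discontinued study treatment early and ends on the last date in the study". That end point applies to everyone, and nothing limits the period by time since last dose.

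Protocol 7.1 says that after permanent discontinuation of study drug "the participant will remain in the study and follow procedures for remaining study visits, as shown in the SoA". SAP 4.6.1 also encourages these participants to stay. The last scheduled visit is Visit 802 at Week 57.

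SAP 4.6.3.1.1 lists the analysis periods, for example "Baseline, 0-6, 0-12, 0-26, 0-52, 12-26, 26-52 weeks, post-treatment period", and the post-treatment period appears for every participant-reported rate and incidence. Rates use negative binomial regression with a log-exposure offset. For Level 2, Level 3 and Level 2/3, total events over total exposure is the fallback if events are too few. Incidence is scored yes or no for at least one event in the period and analyzed by "Logistic regression with treatment and baseline HbA1c as covariates", with no exposure term.

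**The concern.** The post-treatment period matters because of a specific risk. Protocol 6.8.4 gives LY3209590 a half-life of about 17 days and warns that "a careful titration of the daily basal insulin is necessary to prevent hypoglycemia due to overlapping insulin action". That risk belongs to the first weeks after stopping. For completers the window matches it. For a retained early stopper the same window can run for months after the drug has gone, when Protocol 7.1 allows other glucose-lowering treatment.

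Two things follow.

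- **Rates.** The offset corrects for length of follow-up, but not for a rate ratio that fades with time. An early excess on LY3209590 is averaged with later time in which no difference is expected.
- **Incidence.** A 5-week participant and a 50-week participant count alike. If one arm keeps more early stoppers, its incidence rises for that reason alone.

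At stake is the readability of a supportive safety comparison. The 0-52 week hypoglycemia endpoints are unaffected.

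**Working it through.** **Window lengths.** Take first dose = day 0, Visit 31 = day 364, Visit 802 = day 399.

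- Completers: day 365 to day 399 = 35 days = 5.0 weeks. This reproduces the follow-up of approximately 5 weeks stated in Protocol 4.1; the ±7-day window at Visit 802 makes it 4 to 6 weeks.
- Stop on day u, LY3209590: 399 − (u + 11) + 1 = 389 − u days.
- Stop on day u, degludec: 399 − (u + 2) + 1 = 398 − u days.

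| Last dose | LY3209590 | Degludec |
|---|---|---|
| Day 0 | 389 days (55.6 weeks) | 398 days (56.9 weeks) |
| Week 26 | 29.6 weeks | 30.9 weeks |
| Week 50 | 5.6 weeks | 6.9 weeks |

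**Assumptions not in the documents.** A share p of each arm stops and stays to Week 57, with stop times uniform over 52 weeks. Everyone else contributes 35 days. The base rate is 0.5 events/year. The mean stopper window is then 389 − 182 = 207 days (LY3209590) or 398 − 182 = 216 days (degludec).

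**Rate dilution.** Suppose the true ratio is 2.0 in the first 35 post-treatment days for everyone on LY3209590, and 1.0 afterwards. The share of LY3209590 person-time beyond day 35 is approximately

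s = p × (207 − 35) / [(1 − p) × 35 + p × 207],

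and the events-over-exposure ratio is 2 × (1 − s) + 1 × s = 2 − s.

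- p = 2%: s = 3.44 / 38.44 = 9%, ratio 1.91.
- p = 5%: s = 8.60 / 43.60 = 20%, ratio 1.80.
- p = 10%: s = 17.20 / 52.20 = 33%, ratio 1.67.

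The limit of the negative binomial model with offset comes from maximizing its expected log-likelihood over a grid of 400 stop times. For dispersion 1 to 3 it is 1.94-1.96, 1.86-1.90 and 1.76-1.82 at the same three values of p. The model gives long windows less weight than simple pooling does, so it dilutes less. At p = 1.8% (8 of 444, the retrieved-dropout threshold in SAP 4.3.2) it is 1.95-1.96, against 1.92 for events over exposure. Capped at 35 days, both methods return 2.00.

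**Incidence with no true difference.** With Poisson counts, P(event) = 1 − exp(−0.5 × T / 365.25).

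- T = 35 days: 4.68%.
- Averaged over stop times: 23.9% for LY3209590 stoppers, 24.8% for degludec stoppers.
- LY3209590 with p = 10%: 0.90 × 4.68 + 0.10 × 23.9 = 6.60%.
- Degludec with p = 2%: 0.98 × 4.68 + 0.02 × 24.8 = 5.08%.
- Odds ratio: (0.0660 / 0.9340) / (0.0508 / 0.9492) = 1.32.

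At dispersion 3, where P(no event) = (1 + 3m)^(−1/3) and m is the expected count, the incidences are 5.69% and 4.65% and the odds ratio is 1.24.

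| LY3209590 v degludec, stop and stay | Odds ratio (dispersion 3 to 0) |
|---|---|
| 10% v 2% | 1.24-1.32 |
| 5% v 2% | 1.09-1.12 |
| 2% v 10% | 0.80-0.74 |
| 2% v 2% | 1.00 |

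For 10% v 2%, a base rate of 0.25/year gives 1.28-1.34 and 1.0/year gives 1.19-1.29. Capped at 35 days, the odds ratio is 1.00.

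**Precision.** At 444 per arm (888 / 2), 6.60% and 5.08% are about 29.3 and 22.6 participants with an event. The standard error of the log odds ratio is √(1/29.3 + 1/414.7 + 1/22.6 + 1/421.4) ≈ 0.29.

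**The case against.** The other side has several fair points.

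- **No stated endpoint uses this window.** The hypoglycemia endpoints in both documents concern the treatment period, and the analysis periods in Protocol 9.3.5 stop at Week 52. This stands, and it limits the weight of the point.
- **The cap recovers 2.0 by construction.** The excess was assumed to last exactly 35 days and the cap is 35 days. This also stands: the calculation sizes the dilution but does not show that 35 days is the best length. The reason for 35 days is that it is the completers' own follow-up.
- **The rate effect is small.** With about 444 × 35 × 0.5 / 365.25 = 21 events against 43, the log rate ratio has a standard error of about 0.27-0.29. The negative binomial bias is about 0.1 standard errors at 2%, 0.2-0.3 at 5%, and under 0.5 at 10%. This is correct.
- **The incidence shift needs imbalance.** With equal retention of 2% to 10% the odds ratio stays at 0.985-0.997, and 5% v 4% gives only 1.02-1.03. Nothing in the documents predicts 10% v 2%. Discontinuation is reported by arm, so a large imbalance would be visible. Visible is not corrected, however, and retention could differ in an open-label weekly-versus-daily comparison.
- **Other outputs cover the washout.** Level 3 events are reported as serious adverse events and listed. Persistent-recurrent hypoglycemia is assessed to the end of the study. The 4-week post-treatment CGM session has its own analyses. These reduce the chance of missing a signal, but they do not repair the planned diary-based rate and incidence comparisons.
- **The cap does not align washout exactly.** LY3209590 stoppers would contribute about days 11-45 after the last dose, and completers dosed at Week 52 about days 1-35. A 10-day shift at a 17-day half-life leaves 2^(−10/17) ≈ two-thirds of the residual drug. This is a real limitation, but far smaller than mixing 5 weeks with 55.

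**Conclusion.** The concern holds. The unequal windows follow directly from the SAP's date rules and Protocol 7.1, and nothing in either document caps the period or separates completers from early stoppers.

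The consequence is modest. Rate dilution is slight under the planned model if few people stop and stay, and larger under the events-over-exposure fallback. The incidence bias is near zero with equal retention and systematic with unequal retention, though within one study's sampling error. All sizes depend on the assumed retention, stop times, base rate and a 35-day early effect; a constant rate ratio would not be diluted. The stop-and-stay share is the main unknown. This is a change the sponsor should make because it is cheap, not because a main conclusion is at risk.

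**What to change.** In SAP 4.1, keep the existing post-treatment start dates. For the post-treatment rate and incidence comparisons, end the window in both arms 35 days from that start, or at the end of study participation if earlier. Summarize later follow-up off study drug descriptively, by arm. The capped window still does not overlap the treatment period.

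The cost is one amended period definition and one extra table row, with no new data. The compared window will hold fewer events and less person-time, and the LY3209590 misalignment between stoppers and completers should be noted with the table.

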4.2. Participant Dispositions

Reasons for discontinuation prior to randomization including screen failure will be summarized for all participants who sign the informed consent form.

The number and percentage of participants who have completed/discontinued from the study/treatment will be summarized by treatment using the Randomized Population. The individual reasons for discontinuation will also be included in the summary. Comparison will be conducted using the Fisher's exact test.

A listing of the reasons for study/treatment discontinuations will be generated for the Randomized Population. A listing of the randomized treatment for this study will also be provided.

Time to permanent discontinuation of study treatment, time to study discontinuation and time to early discontinuation of study treatment due to AEs (if there is a sufficient number to warrant a summary) will be presented as a figure.

4.3. Primary Endpoint Analysis

4.3.1. Definition of endpoint(s)

The primary endpoint of this study is the HbA1c change from baseline to Week 52 (Visit 31). The HbA1c is reported in unit of % by central laboratory and will be converted to the unit of mmol/mol using the following formula: HbA1c in mmol/mol = 10.93 * HbA1c in % - 23.5 (<http://www.ngsp.org/ifccngsp.asp>). The HbA1c analysis will be conducted for both units.

4.3.2. Main analytical approach

The primary objective is to test the hypothesis that LY3209590 is noninferior to insulin degludec on glycemic control in the targeted study population. The noninferiority test will be based on either of the 2 estimands: **treatment regimen estimand** for the US FDA submission and **efficacy estimand** for registrations in other countries. The full significance level of 0.05 will be used for each estimand.

The following table provides the details of treatment regimen estimand and efficacy estimand.

	Treatment Regimen Estimand	Efficacy Estimand
Analysis Population	All participants in EAS1 with non-missing baseline measure	All participants in EAS2 with non-missing baseline measure and at least one non-missing post-baseline scheduled measure
Analysis Data	All non-missing observations at baseline and Week 52 (Visit 31) regardless of the use of study intervention or rescue medications.	All non-missing observations at baseline and all scheduled post-baseline timepoints during treatment period (that is, Weeks 2, 4, 12, 16, 26, 36 and 52) (prior to the date of last study dose + 10 days for LY3209590 (+1 day for degludec), or the initiation of rescue medication whichever is earlier for participants with intercurrent events).
Missing Data	There may be missing values at Week 52 (Visit 31) due to early study discontinuation. The missing values will be imputed using multiple imputation by the retrieved dropout approach. The retrieved dropout participants are those who discontinue study intervention prior to Week 52 but have non-missing measures at Week 52 in the same treatment arm. If there are only a limited number of retrieved participants that leads to a failure in performing the multiple imputation analysis, such as the model cannot converge, or the number of retrieved dropout participants is small (i.e., at least 1 arm has <8 participants who discontinued study treatment early and have endpoint visit measurements), the missing HbA1c at Week 52 will be imputed by return-to-baseline multiple imputation approach (Qu and Dai 2022)	There may be missing values due to the early discontinuation of study intervention or use of rescue medication. The MMRM model will be used, and the missing values will be handled in the MMRM analysis under the assumption of missing at random.

	Treatment Regimen Estimand	Efficacy Estimand
Analysis Model	
After the imputation, the observed and imputed data will be analyzed by the ANCOVA model using treatment, strata (country, GLP-1 RA treatment at randomization, and SU use at randomization), and baseline value of the dependent variable as independent variables. The statistical inference will be based on the multiple imputation framework by Rubin (1987).
	
The MMRM model will include treatment, strata (country, GLP-1 RA treatment at randomization, and SU use at randomization), visit and treatment-by-visit interaction as fixed effects, and baseline of the dependent variable as a covariate. The Kenward-Roger approximation will be used to estimate denominator degrees of freedom for the MMRM models. An unstructured covariance structure will be used to model the within-participant errors. If this structure fails to converge, the following covariance structures will be used in order until one converges:
 
 1. Toeplitz with heterogeneity 2. autoregressive with heterogeneity 3. compound symmetry with heterogeneous variances 4. Toeplitz 5. Autoregressive 6. compound symmetry without heterogeneous variances.

Abbreviation: ANCOVA = analysis of covariance; MMRM = mixed model repeated measurement.

The 2-sided 95% CI of the LS mean difference (LY3209590 – insulin degludec) in the HbA1c change from baseline to Week 52 (Visit 31) will be estimated. For both estimands, LY3209590 will be declared noninferior to insulin degludec if the upper limit of the 2-side 95% CI for the LS mean difference in the HbA1c (measured in %) change from baseline is below NIM of +0.4%. In addition, the 95% CI for the LS mean difference will be compared to an alternative NIM of +0.3%.

